9.5.4.1.1 Serious Adverse Events (Including Deaths)

Summary of Serious Adverse Events		
Population	:	Safety Set
Group		Study Arm
Contents	:	The number and percentage of patients experiencing a serious adverse event and the number of serious adverse events during the study period.
Output		Summary of Serious Adverse Events -Safety Set- Listing of Serious Adverse Events

Summary of Adverse Events Leading to Death		
Population	:	Safety Set
Group		Study Arm
Contents	:	The number and percentage of patients experiencing an adverse event leading to death during the study period and the number of adverse events leading to death during the study period.
Output		Summary of Adverse Events Leading to Death -Safety Set- Listing of Adverse Events Leading to Death

Confidentiality Statement

Data and information contained in this document are considered to constitute trade secrets and confidential commercial information, and the legal protections provided to such trade secrets and confidential information are hereby claimed under the provisions of applicable law. No part of this document may be publicly disclosed without the written consent of Philip Morris Products S.A.

9.5.4.1.2 Adverse Events Leading to Discontinuation

Summary of Adverse Events Leading to Discontinuation from the Study		
Population	:	Safety Set
Group		Study Arm
Contents	:	The number and percentage of patients experiencing an adverse event leading to discontinuation from the study and the number of adverse events leading to discontinuation from the study.
Output		Summary of Adverse Events Leading to Discontinuation from the Study -Safety Set- Listing of Adverse Events Leading to Discontinuation

9.5.4.2 Device Events

Summary of Device Events		
Population	:	Safety Set
Group		Study Arm (Only IQOS)
Contents	:	
• The “Overview of Device Events” includes a summary of the following items
➤ Subjects with at least one Device event➤ Device Event severity➤ Relation to AE➤ Action taken with the device 
The number and percentage of patients experiencing device events and the number of device events will be summarized by severity and overall, by related parts of device, and by device event term.
 
In addition, the number and percentage of patients and the number of events will be counted by related to AE/not related to AE and by device events severity (major and minor).

Confidentiality Statement

Data and information contained in this document are considered to constitute trade secrets and confidential commercial information, and the legal protections provided to such trade secrets and confidential information are hereby claimed under the provisions of applicable law. No part of this document may be publicly disclosed without the written consent of Philip Morris Products S.A.

Summary of Device Events	
Remarks	: Use data from CRF form “Device Events” and “Device Malfunction and product complaints”. Device event term will be sorted by the order shown in CRF
Output	Overview of Device Events -Safety Set- Summary of Device Events -Safety Set- Listing of Device Events

9.5.4.3 Clinical Laboratory Evaluation

Laboratory Evaluation	
Population	: Safety Set
Group	: Study Arm
Contents	
• Refer to Descriptive statistics• Calculate the value of laboratory parameters for each visit. Also, calculate the change from baseline.
➢ Clinical chemistry➢ Hematology• Also create a graph displaying mean ± standard deviation.• For parameters with the reference range, calculate the number and percentage of subjects in low, normal, or high compared to the reference range.• For urine analysis, calculate the number of subjects in each visit and the number of subjects in each result category by visits.
Analysis variable	: Create for the following categories 
• Clinical chemistry• Hematology• Urine analysis
Output	: Summary of Laboratory Parameters -Safety Set- Summary of Abnormal Laboratory Parameters -Safety Set-

Confidentiality Statement

Data and information contained in this document are considered to constitute trade secrets and confidential commercial information, and the legal protections provided to such trade secrets and confidential information are hereby claimed under the provisions of applicable law. No part of this document may be publicly disclosed without the written consent of Philip Morris Products S.A.

	Series plot of Laboratory Parameters -Safety Set- Summary of Qualitative Urine Parameters -Safety Set- Listing of Laboratory
--	--

9.5.4.4 Medications, Physical Findings, Vital Signs and Other Observations Related to Safety

9.5.4.4.1 Medical History and Concomitant Disease

Summary of Medical History		
Population	:	Safety Set
Group	:	Study Arm
Contents	:	The number and percentage of patients experiencing medical history and the number of medical histories will be counted by MedDRA SOC and PT.
Definitions	:	Medical history is defined as any condition that started and ended prior to Screening (i.e., ended before signing the Informed consent).
Remarks	:	All cases collected on the form for medical history of CRF (MHCAT="MEDICAL HISTORY") will be tabulated.
Output	:	Summary of Medical History -Safety Set- Listing of Medical History/ Concomitant Disease

Summary of Concomitant Disease		
Population	:	Safety Set
Group	:	Study Arm
Contents	:	The number and percentage of patients experiencing concomitant disease and the number of concomitant diseases will be counted by MedDRA SOC and PT.
Definitions	:	A concomitant disease is defined as any condition that started prior to ICF signature and is still ongoing at the end of V1.

Confidentiality Statement

Data and information contained in this document are considered to constitute trade secrets and confidential commercial information, and the legal protections provided to such trade secrets and confidential information are hereby claimed under the provisions of applicable law. No part of this document may be publicly disclosed without the written consent of Philip Morris Products S.A

Summary of Concomitant Disease	
Remarks	: All cases collected on the form for medical history of CRF (MHCAT="CONCOMITANT DISEASE") will be tabulated.
Output	: Summary of Concomitant Disease -Safety Set- Listing of Medical History/ Concomitant Disease

9.5.4.4.2 Prior and Concomitant Medication

Summary of Prior Medication	
Population	: Safety Set
Group	: Study Arm
Contents	: The number and percentage of patients with prior medication/therapy, using the level 1 and 2 ATC codes.
Definition	: Any medication taken within 3 months prior to screening will be considered as prior medication.
Remarks	All cases collected on the form for "Prior and Concomitant Medication" of CRF (CMCAT="PRIOR MEDICATION") will be tabulated.
Output	: Summary of Prior Medication -Safety Set- Listing of Prior and Concomitant Medication

Summary of Concomitant Medication	
Population	: Safety Set
Group	: Study Arm
Contents	: The number and percentage of patients with concomitant medication/therapy, using the level 1 and 2 ATC codes.
Definition	: Any medication which is started prior to screening and is still being taken by the patient at screening or thereafter will be considered as concomitant medication.

Confidentiality Statement

Data and information contained in this document are considered to constitute trade secrets and confidential commercial information, and the legal protections provided to such trade secrets and confidential information are hereby claimed under the provisions of applicable law. No part of this document may be publicly disclosed without the written consent of Philip Morris Products S.A

Summary of Concomitant Medication	
Remarks	All cases collected on the form for "Prior and Concomitant Medication" of CRF (CMCAT="CONCOMITANT MEDICATION") will be tabulated.
Output	: Summary of Concomitant Medication -Safety Set- Listing of Prior and Concomitant Medication

Prior and Concomitant Surgical or Therapeutic Procedures	
Population	: Safety Set
Group	: Study Arm
Remarks	All cases collected on the form for "Prior and Concomitant Procedures" of CRF (PRCAT=" CONCOMITANT THERAPEUTIC PROCEDURE") will be listed.
Definition	: Any Surgical or Therapeutic Procedures taken within 3 months prior to screening will be considered as prior procedures. Any Surgical or Therapeutic Procedures which is started prior to screening and is still being taken by the patient at screening or thereafter will be considered as concomitant procedures.
Output	: Summary of Prior Surgical or Therapeutic Procedures -Safety Set- Summary of Concomitant Surgical or Therapeutic Procedures -Safety Set- Listing of Prior and Concomitant Surgical or Therapeutic Procedures

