6.7 Concomitant Medication

Medications will be allowed and carefully monitored during the study by the Investigator or designee. The Investigator or designee is responsible for the overall safety and well-being of the patient including the overall medical care and medication of the patients during their participation in the study. Any decisions regarding the prescribed medications will be made in the best interest of the patient. Maintenance or changes in treatment of any pre-existing concomitant diseases should be discussed by the Investigator with the treating physician or the patients General Practitioner. Any use of concomitant medication must be fully documented in the source document and transcribed into the Case Report Form (CRF).

Records of medication taken including NRT include the drug name (preferably both generic and trade name), route of administration (e.g., oral, intravenous), total daily dose/unit (e.g., expressed in mg, mL or IU), indication, the start and if applicable, the stop date (day, month and year). Any therapy changes (including changes of regimen) during the study have to be documented. Any concomitant medication that is still being taken by the patient at the EOS will be recorded in the CRF.

Confidentiality Statement

Data and information contained in this document are considered to constitute trade secrets and confidential commercial information, and the legal protections provided to such trade secrets and confidential information are hereby claimed under the applicable provisions of applicable law. No part of this document may be publicly disclosed without the written consent of Philip Morris Products S.A.

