7.4.5 Medical History/Concomitant Disease(s)/Previous and Ongoing Medications

Relevant medical history, any concomitant disease, and previous and ongoing medications will be documented at V1 for all patients. It will be responsibility of the Investigator or designee to collect the relevant medical records for each patient necessary for the purposes of this study.

Medical history is defined as any condition that started and ended prior to Screening. A concomitant disease is defined as any condition that started prior to ICF signature and is still ongoing at the end of V1. After V1, each concomitant disease will be followed-up at each visit to check if it is still ongoing or not.

Previous medication taken within 3 months prior to screening and any ongoing medication at screening needs to be documented. Any medication which is started prior to Screening and is still being taken by the patient at screening or thereafter will be considered as concomitant medication. This applies to both prescription and over-the-counter products.

Confidentiality Statement

Data and information contained in this document are considered to constitute trade secrets and confidential commercial information, and the legal protections provided to such trade secrets and confidential information are hereby claimed under the applicable provisions of applicable law. No part of this document may be publicly disclosed without the written consent of Philip Morris Products S.A.

Any use of a concomitant medication must be fully documented in the Source Document and CRF. Therapy changes (including changes of regimen) during the study have to be documented. If a concomitant medication is still being taken by the patient at the end of the study, this will be recorded in the CRF.

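### The SAP's definition of concomitant medication and procedures has no class for treatments first started after screening, and it disagrees with the SAP's own selection rule and with the safety endpoint it serves

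*SAP*

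**What the plan says.** SAP 9.5.4.4.2 sets two classes for medication:

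- Prior: "Any medication taken within 3 months prior to screening will be considered as prior medication".
- Concomitant: "Any medication which is started prior to screening and is still being taken by the patient at screening or thereafter".

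Procedures follow the same pattern. Prior is "Any Surgical or Therapeutic Procedures taken within 3 months prior to screening will be considered as prior procedures" and concomitant is "Any Surgical or Therapeutic Procedures which is started prior to screening and is still being taken by the patient at screening or thereafter".

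The Remarks rows in the same boxes work differently. For medication, each table takes every record whose CMCAT value matches (PRIOR MEDICATION or CONCOMITANT MEDICATION), with no condition on dates. For procedures, the row names a single PRCAT value, CONCOMITANT THERAPEUTIC PROCEDURE, and says those records are to be listed. The Output row nevertheless asks for separate prior and concomitant summaries.

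The medication sentence comes from Protocol 7.4.5, which has the same restriction: "Any medication which is started prior to Screening and is still being taken by the patient at screening or thereafter". In that section it follows the instruction for the V1 record: "Previous medication taken within 3 months prior to screening and any ongoing medication at screening needs to be documented". Protocol 6.7 covers the study itself: "Any therapy changes (including changes of regimen) during the study have to be documented", with start and stop dates.

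SAP 3.2 lists concomitant medications under safety objective 4, for the full duration of the study. Protocol 12.8 plans their incidence and frequency by arm.

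**The concern.** The endpoint is meant to describe medication throughout follow-up, but the definition admits only treatment that was already running at entry. Treatment begun before screening is largely a baseline characteristic. Treatment begun after allocation is the part that could differ between arms because of the assigned product. New cardiovascular drugs are an example: they bear on how the systolic and diastolic blood pressure results under objective 6 are read.

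Two things could go wrong. New starts could be left out of the concomitant tables by arm. Treatments ongoing at entry could appear in both tables, which would blur the line between them. Protocol 12.1 adds weight, because it requires the analyses in a signed SAP to be performed as described. A programmer should not have to disregard a Definition row to get the intended table.

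**Working it through.** The plan gives no figure to reproduce here. The check is to apply the written definitions to each possible timing and compare the result with the rest of the plan.

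**Reading the sentence.** It sets two conditions joined by *and*: started before screening, and still in use at or after screening. The closing words about later time qualify continued use, not the start, so they do not bring in new treatments.

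**Classification under the definitions as written**

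| Timing of treatment | Prior? | Concomitant? |
|---|---|---|
| Taken in the 3 months before V1 and stopped before V1 | Yes | No |
| Started before V1 and still in use at V1 | Yes, if in use during those 3 months | Yes |
| First started at or after V1, up to V8 | No | No |

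The same table holds for procedures.

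**Length of the unclassified window.** Screening of up to 28 days plus an Investigational Period of up to 3 years (Protocol 4.3) gives about 1 + 36 = 37 months, the protocol's own total of 3 years and 1 month.

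**Is there another class for new starts?** None was found in either document. The three changes in SAP section 7 concern stratified analyses, omics profiles and the albumin to creatinine ratio. Concomitant disease in SAP 9.5.4.4.1 also requires onset before consent, but there the restriction does no harm: Protocol 8.2.2.2 sends new or worsening conditions to the adverse event record. New medications have no such second home.

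**Are the data there?** Yes. Protocol Appendix 1 records medication at V1 to V8, and Protocol 6.7 requires dates and changes.

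**Does the Remarks row settle the matter?**

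- Medication: if sites enter a new on-study drug under CONCOMITANT MEDICATION, it reaches the table despite the definition. If CMCAT is assigned or cleaned according to the definition, it does not. The documents do not say which applies, so the Definition and Remarks rows can produce different tables from the same data.
- Procedures: with one PRCAT value named, the category cannot separate prior from concomitant. The date definition is the only stated way to split the two required summaries, and it has no place for a procedure begun after screening.

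**The case against.** The strongest reply is that the medication table is built by the Remarks row, which takes all records in the category. The SAP names only two CMCAT values, and a drug started on study does not fit the prior one, so sites would naturally enter it as concomitant. On that reading the definition is clumsy and nothing is lost. This is plausible, but it is an inference about CRF practice that the documents do not state, and it does not cover procedures.

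Several further points stand:

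- Collection is intact and listings of medication and procedures are planned, so only summaries are exposed.
- A reader might infer that nicotine replacement begun in a quit attempt would go unseen. It would not: SAP 9.4 summarises it from the diaries by arm, V3 to V8.
- A reader might infer that the SAP introduced the restriction. Protocol 7.4.5 carries the same medication sentence.
- Procedures are not a named safety endpoint. Open and endovascular AAA repair have their own analyses in SAP 9.5.2.1.1 and 9.5.2.1.2 and are unaffected.
- The study is descriptive and tests no hypothesis.

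**Conclusion.** The point holds as a defect of definition. The SAP's rule for concomitant treatment contradicts the scope of the endpoint it serves. It also disagrees with the medication Remarks row, and for procedures it is the only stated way to split the two summaries. The exposed period is everything from screening to V8, up to about 37 months per patient.

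Two stronger readings are tempting. One is that every treatment started on study is excluded from the tables. The other is that every medication ongoing at entry is counted twice. Both follow only if records are assigned by the Definition row and the CRF category is ignored. The documents do not establish that, so both remain possibilities. The number of patients affected cannot be estimated either, because neither document gives a rate of new treatment or says how CMCAT and PRCAT are assigned.

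The primary growth-rate analysis is not touched. What is at risk is the by-arm summary of one listed safety endpoint, together with the procedure summaries.

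**What to change.** In SAP 9.5.4.4.2, for both medication and procedures:

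- Define prior as stopped before screening (V1). The existing 3-month look-back can stay.
- Define concomitant as ongoing at V1, or started at or after V1 up to the end of study.
- Make the Remarks rows consistent with these definitions. State how CMCAT and PRCAT relate to them, and give the procedures box a rule that separates its two summaries.
- Record the departure from the Protocol 7.4.5 sentence in SAP section 7.

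Optionally, flag medications started after randomisation (IQOS and CIG) or enrolment (SC), by arm. A separate row for nicotine replacement is not needed, given SAP 9.4.

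The cost is a few SAP sentences, a small amount of programming and one entry in section 7. If records are classed by date, a line on incomplete dates is also needed, since SAP 9.1.5 gives none. No new data and no patient burden are involved. SAP section 1 requires amendments to be final before database lock; a later change would have to be described in the study report.

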9.5.4.4.3 Physical Examination

Summary of Physical Examination	
Population	: Safety Set
Group	: Study Arm
Contents	Calculate the number of subjects in each visit and the number of subjects in each result category by visits.

Confidentiality Statement

Data and information contained in this document are considered to constitute trade secrets and confidential commercial information, and the legal protections provided to such trade secrets and confidential information are hereby claimed under the provisions of applicable law. No part of this document may be publicly disclosed without the written consent of Philip Morris Products S.A

Output	:	Summary of Physical Examination -Safety Set- Listing of Physical Examination
--------	---	---

9.5.4.4.4 Vital Signs

Vital Signs		
Population	:	Safety Set
Group	:	Study Arm
Contents		
• Refer to Descriptive statistics• Calculate the value of vital sign parameters for each visit. Also, calculate the change from baseline.
➤ Systolic blood pressure➤ Diastolic blood pressure➤ Pulse rate➤ Respiratory rate• Also create a graph displaying mean ± standard deviation.
Output	:	Summary of Vital Signs -Safety Set- Series plot of Vital Signs -Safety Set- Listing of Vital Signs

9.5.4.4.5 Electrocardiogram

Summary of ECG		
Population	:	Safety Set
Group	:	Study Arm
Contents		
• Refer to Descriptive statistics• Calculate the value of ECG parameters for each visit. Also, calculate the change from baseline.

Confidentiality Statement

Data and information contained in this document are considered to constitute trade secrets and confidential commercial information, and the legal protections provided to such trade secrets and confidential information are hereby claimed under the provisions of applicable law. No part of this document may be publicly disclosed without the written consent of Philip Morris Products S.A.

		
• Calculate the number of subjects within each visit and the number of subjects in each result category by visits.
Output	:	Summary of Electrocardiogram -Safety Set- Summary of Qualitative Electrocardiogram -Safety Set- Series plot of Electrocardiogram -Safety Set- Listing of Electrocardiogram

9.5.4.4.6 Other Safety Assessments

Listing of Chest X-Ray		
Population	:	Safety Set
Group	:	Study Arm
Output	:	Listing of Chest X-Ray

10 ANALYSES AND REPORTING

10.1 Interim Analyses and Data Monitoring

For this study, data reviews by IDMC members will be performed one year and two years after the first patient has been randomized. Sponsor will be informed at least with meeting minutes. All data reviews by IDMC members will focus on safety, study quality, product use exposure, and disease characteristics and progression.

10.2 Safety Reporting

Not applicable

10.3 Topline Results

Not applicable

Confidentiality Statement

Data and information contained in this document are considered to constitute trade secrets and confidential commercial information, and the legal protections provided to such trade secrets and confidential information are hereby claimed under the provisions of applicable law. No part of this document may be publicly disclosed without the written consent of Philip Morris Products S.A

10.4 Final Analyses

Not applicable

10.5 ClinicalTrials.Gov Reporting

The planned TFLs contain the necessary information for reporting to ClinicalTrials.gov.

11 DATA PRESENTATION

Data presentation details are provided in a separate TFL mock shell document, based on the PMI style guide provided by PMI.

13 APPENDICES

13.1 Study Assessments

Not applicable

13.2 Tables, Figures & Listings

The list of TFLs is provided in a separate TFL mock shell document.

Confidentiality Statement

Data and information contained in this document are considered to constitute trade secrets and confidential commercial information, and the legal protections provided to such trade secrets and confidential information are hereby claimed under the provisions of applicable law. No part of this document may be publicly disclosed without the written consent of Philip Morris Products S.A.
